3. Subjects with any clinically significant abnormalities as determined by medical history, physical exam, clinical and lab evaluation suggestive of an underlying disease state that may, in the opinion of the investigator, confound the results of study, increase risk to the subject, or lead to difficulty complying with the protocol.
4. Subjects on chlorpromazine, PDE-5 inhibitors, nitrites and any medication with CNS effects with the exception of antipsychotic drugs (other than chlorpromazine) anticholinergics, b-adrenergic antagonists, amantadine, biperiden, diphenhydramine, lorazepam, zolpidem, and temazepam.
5. Medications which in the opinion of the PI, and in conjunction with the medical monitor, may be expected to significantly interfere with the metabolism or excretion of sodium nitroprusside, and/or may be associated with a significant drug interaction with sodium nitroprusside that may pose a significant risk to subjects' health and/or confound the study data.
6. Pregnant or breast-feeding patients. Women of childbearing potential must have a negative pregnancy test performed at screening visit prior to randomization and prior to baseline at visits 3 and 6. Women enrolled in this trial must use adequate birth control.
7. Subjects with a current (within the last 3 months) DSM-IV-TR diagnosis of alcohol or substance use disorder or dependence (excluding nicotine) as established by the clinical assessment (SCID) at the screening visit will be excluded.
8. Has tested positive for any of the following: cannabis, opioids, cocaine, amphetamines, barbiturates methadone, methamphetamine and phencyclidine at the screening or baseline visits. If positive, the urine drug toxicology screen may be repeated once based on investigator judgment, but due to safety concerns, the result must be negative for the subject to continue in the study.

9. Subjects at imminent risk of suicide or injury to self or others, as per the opinion of the investigator, or history of significant suicide attempt within the last 6 months as per C-SSRS.
10. Subjects that have taken an investigational drug or taken part in a clinical trial within 30 days prior to screening.
11. Any other reason that, in the opinion of the investigator, would compromise patient safety or integrity of the study

Table 1- Exclusionary Safety Values of Potential Clinical Concern

Hematology	
Leukocytes	<2 or >17.5 x 10 ³ /mm ³
Platelets	<75 or >700 x 10 ³ /mm ³
Comprehensive Metabolic Panel	

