Nitroprusside infusion has been widely used for decades to control profound hypertension and most recent reviews have concluded that it is quite safe at doses less than 2 $\mu\text{g}/\text{kg}/\text{min}$. The most important adverse reactions to sodium nitroprusside are the avoidable ones of excessive hypotension and cyanide toxicity. (Package Insert <http://medlibrary.org/lib/rx/meds/nitropress/> - last revised January 16, 2014).

No adverse effects were observed in 10 schizophrenia subjects who received nitroprusside 0.5 $\mu\text{g}/\text{kg}/\text{min}$ in the study by Hallak et al., including no cases of hypotension despite administering nitroprusside to two subjects treated with chlorpromazine (500 mg/d and 300 mg/d); chlorpromazine has the greatest propensity for orthostatic hypotension of any antipsychotic and subjects taking this drug will be excluded from the study. Nitroprusside was also added to high-dose ziprasidone (240 mg/d) and high dose risperidone (8 mg/d) without measurable effects on blood pressure or EKG.

The potential for cyanide toxicity is greatest when more than 500 $\mu\text{g}/\text{kg}$ of sodium nitroprusside is administered faster than 2 $\mu\text{g}/\text{kg}/\text{min}$, as cyanide is generated faster than the unaided patient can eliminate it. Cyanide toxicity will be avoided in this study as the dose administered is very low, and individuals with renal disease will be excluded. Also, the study treatment will be infused within 3 hours of preparation as sodium nitroprusside is stable in solution for 24 hours.

Subjects will be continuously monitored for adverse effects during the infusion and blood pressure and heart rate will be taken and recorded 2 hours post infusion.

Given that subjects with renal disease, a history of orthostatic hypotension or medications that destabilize blood pressure will be excluded from the study, and that the infusion rate of SNP for subjects randomized to active drug in this study will be very low (0.5 $\mu\text{g}/\text{kg}/\text{min}$), the risk of excessive hypotension and cyanide toxicity is very low.

H. STUDY ASSESSMENTS – PLAN AND METHODS

Study Conduct

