Given that subjects with renal disease, cardiac disease, hypotension or medications that destabilize blood pressure will be excluded from the study, and that the infusion rate of SNP for subjects randomized to active drug in this study will be low (0.5 $\mu\text{g}/\text{kg}/\text{min}$), the risk of excessive hypotension and cyanide toxicity is low.

Sodium nitroprusside does have some potential for drug-drug interactions. The hypotensive effect of sodium nitroprusside is augmented by that of most other hypotensive drugs, including ganglionic blocking agents, negative inotropic agents, and inhaled anesthetics. Subjects taking any of these drugs will be excluded from the study. Patients will also be advised not to take these medications during the course of the study.

Infusion Monitoring and Discharge Procedures

The study treatment will be infused with a volumetric infusion pump and the blood pressure of a subject will be continuously monitored by a cardiologist, anesthesiologist, or medically qualified designate as per institutional guidelines. A study physician will be available for consultation on any participant safety issues that arise during the infusion. Each participant will be allowed to rest in a semi-recumbent position. Each subject will receive an intravenous line. The study treatment will be infused with a volumetric infusion pump and the blood pressure of a subject will be continuously monitored by a cardiologist, anesthesiologist, or medically qualified designate as per institutional guidelines. To maintain the double blind, each subject will receive an infusion for 4 hours. Nitroprusside or placebo will be administered at the dose specified in the randomization scheme. Subjects will have one-to-one nursing care during the infusion of the study treatment.

The assigned nurse or medically qualified designate will perform the following monitoring procedures, as developed by the consulting cardiologist:

- Pre-Infusion: 12-Lead ECG (Time -1 to Time 0, baseline)
- During Infusion:
 - 12-Lead ECG @ 30 min
- Post-Infusion:
 - 12-Lead ECG @ 60 min post-infusion
- Vital Signs: BP, HR and O2 sat (same arm, non-IV arm)
Pre-Infusion (baseline)
During Infusion:
 - Q5 min Xs 30 minutes then Q10 min Xs 3.5 Hrs (210 min)
- Post-Infusion:
 - Q5 min Xs 30 minutes then Q10 min Xs 1.5 Hrs (90 min)

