The hypotensive effect of sodium nitroprusside is augmented by that of most other hypotensive drugs, including ganglionic blocking agents, negative inotropic agents, and inhaled anesthetics. Subjects taking any of these drugs will be excluded from the study.

Concomitant Therapy

The subject may not have adjustment of psychotropic medications except for benzodiazepines or anticholinergic agents if deemed absolutely necessary by the Investigator for relief of transient symptoms. (See Appendix 3: Medications Allowed and Not Allowed as Concomitant Medications). Subjects must be questioned at each study visit concerning any new medications or changes in current medications including over-the-counter medication and topical medication. All medications and therapies administered or taken by the subject beginning 30 days prior to signing the ICF and throughout the study will be recorded. The subjects' antipsychotic medication type should have remained unchanged for at least eight (8) weeks prior to screening into the study, at constant dose for at least 4 weeks, and should be expected to remain unchanged during the study.

For each medication and non-study treatment, the following will be documented:

- Medication/treatment name (generic name may be used if trade name is unknown)
- If an anti-psychotic medication, whether typical or atypical.
- Dose, unit, and frequency of dosing (individual dosages, not total daily dose). Note: Each new dose of medication should be recorded as a separate entry, with the exception of medications that are given on a sliding scale. For these, it is acceptable to enter the range of the dosage, including the start and stop dates for which the specified dosage range was used.
- Route of dosing
- Indication for use
- The start date
- The stop date (if medication/therapy is not ongoing)

Discontinuation from Study Treatment

Every effort will be made to keep the patient in the study for the full study period consisting of two phases of treatment with follow-up assessments. Acceptable reasons for early discontinuation include the following: 1) request of patient, 2) decision of physician, 3) serious adverse event, and 4) protocol violation.

Medical Reasons for Discontinuation:

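### The protocol text excludes subjects on drugs that add to nitroprusside's hypotensive effect, but Appendix 3 and criterion 4 leave room for several such drugs, depending on how the exclusion is read

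*Protocol*

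**What the plan says.** **The exclusion.** Protocol section I, Possible Drug Interactions, opens with "The hypotensive effect of sodium nitroprusside is augmented by that of most other hypotensive drugs", gives three classes as examples, the first being ganglionic blockers, and closes: "negative inotropic agents, and inhaled anesthetics. Subjects taking any of these drugs will be excluded from the study". Section H, Safety Profile of Sodium Nitroprusside, repeats the rule and adds: "Patients will also be advised not to take these medications during the course of the study".

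**The risk statements.** Section G, Rationale for the Inclusion/Exclusion Criteria, supports its low-risk judgement partly by saying that subjects with "a history of orthostatic hypotension or medications that destabilize blood pressure will be excluded from the study". Section H makes the same argument, with the drug exclusion as one ground among several: "renal disease, cardiac disease, hypotension or medications that destabilize blood pressure will be excluded from the study, and that the infusion rate".

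**The permitted list.** Section I, Concomitant Therapy, sends the reader to the appendix: "See Appendix 3: Medications Allowed and Not Allowed as Concomitant Medications". There, anti-hypertensives are barred for episodic use and allowed for chronic use, with only diltiazem and verapamil ruled out. Chronic diuretics and alpha-1 blockers (the latter in the prostatic hyperplasia row) are allowed under footnote b, which requires 3 months of use and a dose stable for 1 month. General anesthetics are allowed episodically, with a request to report the medical condition to the coordinating center.

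**The numbered criteria.** Criterion 4 bars drugs with CNS effects but lists exceptions, among them "b-adrenergic antagonists, amantadine, biperiden, diphenhydramine, lorazepam, zolpidem, and temazepam". Criteria 3, 5 and 11 rest on judgement. Criterion 3, for example, turns on abnormalities that may, "in the opinion of the investigator, confound the results of study, increase risk to the subject". Criterion 5 covers drugs that may interact significantly with nitroprusside, as judged by the PI together with the medical monitor.

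**Systolic pressure (SBP) during the infusion.** Section H, Infusion Monitoring and Discharge Procedures, gives one set of rules and section I, Dose Modification during Treatment, gives another. Section I, Medical Reasons for Discontinuation, says that the section H rules decide when an infusion is discontinued.

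**The concern.** The protocol names excessive hypotension as one of the two most important adverse reactions to the drug. Its text states an unconditional exclusion aimed at that risk, while the appendix that sites are sent to allows drugs which that exclusion may cover. Two sites could then reach opposite decisions on the same subject, each with support in the protocol. The advice during the study divides in the same way: section H tells patients to avoid drugs whose chronic use Appendix 3 may permit.

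For a subject admitted this way, one of the stated grounds for low risk may not hold. A smaller effect falls on the analysis sets. Table 3 lists enrolling an ineligible subject without an exception as a major violation, and the per-protocol population leaves out major violations. Membership of that supportive population could therefore depend on which text is applied. The ITT analysis does not depend on it.

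The two sets of SBP rules are a lesser matter: bedside staff have two instructions where one would do.

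**Working it through.** No power or alpha calculation applies. The check sets the sections side by side.

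**Step 1. What does the exclusion cover?** Two readings are open. On the broad reading it covers hypotensive drugs generally, with the three classes as examples. On the narrow reading it covers only those three classes.

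| Drug class | Where it is allowed | Broad reading | Narrow reading |
|---|---|---|---|
| Anti-hypertensives other than diltiazem and verapamil | Appendix 3, chronic use, no footnote as printed | Conflict | Not barred as a class |
| Diuretics, chronic | Appendix 3, footnote b | Conflict | Not barred |
| Alpha-1 blockers | Appendix 3, footnote b | Conflict | Not barred |
| General anesthetics, episodic | Appendix 3, with report to the coordinating center | Tension, so far as inhaled | Same tension |
| b-adrenergic antagonists | Exception in criterion 4; not barred by the anti-hypertensives row | Position not stated | Open: documents do not say whether they are negative inotropes |

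Three classes conflict on the broad reading. The last two rows remain unresolved even on the narrow one.

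**Step 2. Does a numbered criterion settle it?** Of the 11 exclusion criteria in section G, 0 name anti-hypertensives. Three (3, 5 and 11) could exclude such a subject by judgement. Criterion 5 is the closest fit, because it concerns interactions with nitroprusside directly.

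**Step 3. SBP rules.**

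| SBP (mm Hg) | Infusion Monitoring, run-in | Infusion Monitoring, full rate | Dose Modification |
|---|---|---|---|
| 90 or more | Continue | Continue | Continue |
| 81 to 89 | Stop | Half rate for 15 min; abort if it stays there | Half rate |
| 80 | Stop | No action listed | Half rate |
| Below 80 | Stop | Stop | Stop |

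- Run-in: one section stops and the other halves at 89 − 80 + 1 = 10 whole-number values.
- Full rate, first step at 81 to 89: the two agree, since 50% × 0.5 = 0.25 µg/kg/min, which is the run-in rate.
- Full rate, pressure still low after 15 minutes: one section aborts and the other gives no further step, at 89 − 81 + 1 = 9 values.
- Exactly 80 at full rate: 1 value without an action in the section H list; Dose Modification supplies one.

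The first and third differences concern stopping, which Medical Reasons for Discontinuation assigns to section H.

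**The case against.** The strongest reply is that the exclusion means only the three named classes. A rule about most hypotensive drugs cannot be applied at screening, and ruling out diltiazem and verapamil may be an attempt to apply the negative-inotrope rule. On that view Appendix 3 allows ordinary anti-hypertensives on purpose. This reading is tenable. A reader might infer that the anti-hypertensives row flatly contradicts the text, and the documents do not support that much. Nor can anti-hypertensives be singled out, since the reading that catches them also catches diuretics and alpha-1 blockers. The reply does not explain the general-anesthetics row, although in practice that row matters little, and it leaves the position of b-adrenergic antagonists unstated.

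It can also be said that established chronic treatment does not destabilize pressure, and that Appendix 3 bars episodic anti-hypertensive use. That is arguable, but the protocol does not say it. The missing stability footnote is weak evidence either way, because a marker may have been lost in text extraction.

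Other safeguards are real: criterion 5 with the medical monitor, the bar on symptomatic orthostatic hypotension, the disease exclusions, the low rate, the half-rate run-in, continuous pressure monitoring and one-to-one nursing. They limit the clinical consequence. They do not make a judgement-based criterion equivalent to an unconditional exclusion.

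On SBP the objection largely succeeds. The stopping differences are settled in favour of section H, and the protocol as a whole has an action at exactly 80.

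**Conclusion.** The eligibility inconsistency holds and should be fixed. It covers three drug classes on the broad reading. On the narrow reading, one permitted row (general anesthetics) and one unclassified group (b-adrenergic antagonists) remain. On either reading no numbered criterion states the rule, so eligibility can depend on which section a site follows.

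The documents do not give the number of screened subjects who would take these drugs, so exposure cannot be sized. A reader might infer that such subjects would be unprotected, or that hypotension would be frequent. Neither follows: several grounds for low risk are unaffected, and no event rate can be derived. A reader might also infer that criterion 4 admits a negative inotrope outright. That would need a pharmacological classification that the documents do not give.

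The SBP duplication is minor, because every competing action lowers or stops the infusion. Sample size, power, type I error and the primary ITT test are unaffected.

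**What to change.** Make one drug list govern.

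- **Default:** bring Appendix 3 into line with the exclusion stated in Safety Profile and Possible Drug Interactions, and add a numbered exclusion criterion that names the barred classes and states the position of b-adrenergic antagonists. Reconcile the general-anesthetics row at the same time.
- **Alternative, if stable chronic blood-pressure drugs are meant to be allowed:** apply footnote b to the anti-hypertensives row, and correct the exclusion and risk statements in Rationale for the Inclusion/Exclusion Criteria, Safety Profile and Possible Drug Interactions. The position of b-adrenergic antagonists still needs stating.

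The sponsor's medical lead should choose between these.

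In the same amendment, replace the SBP sentence in Dose Modification during Treatment with a cross-reference to Infusion Monitoring and Discharge Procedures, and set an action at exactly 80 mm Hg in the full-rate list there. The two edits must go together, since the sentence being removed is the only one that now covers 80 at full rate. If the stop moves to 80, decide whether the saline-bolus threshold, now below 80, moves with it.

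The cost is protocol wording and site retraining, with slightly narrower recruitment if classes are barred.
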